Study visits will be conducted at 2, 4, 6, and 12 weeks after randomization and at approximately 12-week intervals thereafter. Following the 110-week blinded treatment period, treatment with study medication will be discontinued for 4 weeks. At this time, the Investigator should resume standard-of-care treatment, including RAAS inhibitor treatment. Where possible, the same treatment regimen the patient was on at study entry (ie, the same ACEI and/or ARB at the same dose[s]) should be used unless, in the Investigator's opinion, an alternative treatment approach is warranted. The Investigator may make additional adjustments in anti-hypertensive medications if considered necessary to adequately control blood pressure. Patients will return to the site for the Week 114 visit after study medication has been discontinued (see [Table 1](#) and [Section 15.1](#)).

[figure not shown]
Patients who complete the double-blind period may be eligible to enroll in the open-label extension period.

Sparsentan or irbesartan concentrations (and possibly metabolites) in plasma will be evaluated. At specified visits, 1 trough sample will be obtained pre-dose in the clinic.

The primary analysis of proteinuria will be performed after the last patient randomized has undergone the Week 36 visit. Subsequently, all patients will continue to be followed on an intent-to-treat basis to Week 114 for the longer-term assessment of eGFR rate of change. Unless otherwise specified, endpoints will use the last pre-treatment value available prior to the first dose of study medication as baseline.

Flow chart and table depicting the double-blind period are provided in [Figure 1](#) and [Table 1](#).

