### 6.2.2. Open-label Extension Period Design

Patients may be evaluated for eligibility to participate in the open-label extension period using assessments from the Week 110 visit as screening assessments. Patients with an eGFR value of  $<30$  (but  $>20$ ) mL/min/1.73 m^2 will be eligible for participation in the open-label extension period at the discretion of the Investigator but will require close monitoring of eGFR and serum potassium (see [Section 7.2.2](#)).

[figure not shown]
For patients who agree to participate in the open-label extension period and meet the eligibility criteria (see [Section 7.2](#)), the Week 114 visit will also serve as the baseline visit (Day 1) for the open-label extension period. Standard-of-care treatment (ACEI and/or ARB therapy) and any other prohibited concomitant medications will be discontinued before the Week 114 visit (see [Section 15.2.1](#)). The final dose of an ACEI and/or ARB therapy should be taken on the day before the Week 114 visit. At the Week 114 visit, patients will sign a new informed consent (if not completed previously at Week 110) for the open-label extension period and will begin taking open-label sparsentan. All Week 114 (baseline visit) evaluations must be completed prior to the first dose of open-label sparsentan.

At Week 114, the starting dose is 1 tablet (200 mg) for all patients. At Week 116, the patient's dose will be titrated to either 2 tablets ( $2 \times 200$  mg) or 1 tablet ( $1 \times 400$  mg, when available), if tolerated and determined safe by the Investigator. For details regarding dose titration in the open-label extension period, see [Section 8.1.2](#); for details regarding dose modifications, see [Section 8.3.2](#).

As in the double-blind period, additional anti-hypertensive agents are allowed during the open-label extension period to maintain blood pressure as close as possible to 125/75 mmHg, with the exception of those that inhibit the RAAS and endothelin systems (see [Section 8.3.2](#) for concomitant medication considerations).

Patients will participate in the open-label extension period for up to 156 weeks (see [Figure 2](#)) for a total of 270 weeks in the study (ie, double-blind and open-label extension periods). If sparsentan becomes commercially available during the open-label extension period, patients may transition out of the study onto commercial product before the end of the open-label extension period.

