#### **6.4. Patient Completion and Overall Study Completion**

Each patient will participate in the double-blind period for up to 28 days during screening, followed by 110 weeks of blinded treatment. At the end of the 110-week treatment period, treatment with study medication will be discontinued. Patients will return to the site for the end-of-blinded-treatment-period visit, 4 weeks after study medication has been discontinued. Thus, patients will participate in the study for a total of approximately 118 weeks.

A patient will be considered as having completed the double-blind period regardless of whether the patient is on or off study medication if the patient is followed until Week 114.

Patients who successfully complete the Week 114 visit will complete the assessments listed in the Schedule of Events ([Table 15.1-1](#) and [Table 15.1-2](#)). The visit data, including disposition of the patient, will be recorded on the appropriate eCRF.

Patients who complete the double-blind period may be eligible to enroll in the open-label extension period.

Eligible patients may participate in the open-label extension period for up to 156 weeks. If sparsentan becomes commercially available during the extension period, patients may transition out of the study onto commercial product before the end of the open-label extension period.

The study will be considered complete when the last patient completes his/her final visit.

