**Table 15.1-2. Double-blind Period: Schedules of Study Events from Week 48 Through End of Double-blind Period**

	Blinded Treatment Period							End-of-Blinded Treatment Period
Week	Week 48	Week 58	Week 70	Week 82	Week 94	Week 106	Week 110/EOT/ET a	Week 114
Visit	9	10	11	12	13	14	15	16
Visit Window	± 14 days	± 14 days	± 14 days	± 14 days	± 14 days	± 14 days	± 14 days	- 7/ + 14 days
Full Physical Examination		X					X	
Targeted Physical Examination	X		X	X	X	X		X
Peripheral Edema Assessment b	X	X	X	X	X	X	X	X
Vital Signs c	X	X	X	X	X	X	X	X
Clinical Laboratory Assessments Panel A d	X	X	X	X	X	X	X	X
Lipid Panel e	X	X	X	X	X	X	X	X
NT-proBNP	X	X	X	X	X	X	X	X
Aldosterone, Renin, Endothelin	X		X		X		X	X
Biorepository Samples (blood and urine, if consented)		X		X			X	X
Coagulation Tests (Prothrombin Time, INR)	X		X				X	
Quantitative Urinalysis (24-hour collection) f	X	X	X	X	X	X	X	X
Calculate eGFR g	X	X	X	X	X	X	X	X
PK Plasma Levels h	X		X		X		X	
Pregnancy Test i	X	X	X	X	X	X	X	X
QoL Questionnaires j	X		X		X		X	
Dispense Urine Pregnancy Tests k	X	X	X	X	X	X	X	
Informed Consent for OLE l							X	X
Study Medication Dispensing m	X	X	X	X	X	X		
Study Medication Accountability	X	X	X	X	X	X	X	
Adverse Event Assessment	-----Continuous Monitoring -----							
Concomitant Medications/Therapies	-----3 Months prior to screening followed by Continuous Monitoring -----							

Abbreviations: ALP = alkaline phosphatase; ALT = alanine aminotransferase; AST = aspartate aminotransferase; BUN = blood urea nitrogen; CKD-EPI = Chronic Kidney Disease Epidemiology; eCRF = electronic case report form; eGFR = estimated glomerular filtration rate; EOT = End-of-Treatment; EQ-5D-5L = EuroQol 5-dimension, 5-level QoL Questionnaire; ET = Early Termination; HDL = high-density lipoprotein; INR = international normalized ratio; KDQoL-36 = Kidney Disease QoL Questionnaire; LDL = low-density lipoprotein; MCH = mean corpuscular hemoglobin; MCHC = mean corpuscular hemoglobin concentration; MCV = mean corpuscular volume; NT-proBNP = N-terminal prohormone of brain natriuretic peptide; OLE = Open-label Extension; PK = pharmacokinetics; QoL = Quality of life; SF-12 = 12-Item Short Form Health Survey (QoL questionnaire); WBC = white blood cell; WOCBP = women of childbearing potential.

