- f Sample will be collected 24 hours immediately prior to the visit. Patients who forget to collect this sample the 24 hours immediately prior to the visit may collect and return it within the visit window. Protein and albumin excretion, creatinine, sodium, and urea will be measured from this sample.
- g Calculated using the CKD-EPI formula based on age, sex, race, and serum creatinine values from the visit.
- h A blood sample for plasma PK will be drawn prior to study medication administration. Once EOT is completed for a patient, PK samples will not be collected.
- i WOCBP only. Urine pregnancy tests will be performed at all visits and monthly between visits. A positive urine pregnancy test will be confirmed by a serum test.
- j QoL questionnaires should be completed prior to any other assessment. The questionnaires will be the KDQoL-36 (which consists of the first 12 questions of the SF-12 and 24 questions [questions 13-36] from the KDQoL-36) and the EQ-5D-5L. If the questionnaires were NOT completed at baseline for the double-blind period (Day 1), the patient should not complete them for the rest of the double-blind period. Patients participating in the open-label extension period who did not complete the questionnaires at Day 1 of the double-blind period should complete them at Week 114 (as baseline assessments for the open-label extension) and throughout the open-label extension.
- k Sites will provide WOCBP with enough tests to conduct pregnancy testing once per month until the next scheduled study visit and will contact these patients monthly to confirm that the pregnancy test has been performed and the results are negative.
- l Patients who may be eligible for the open-label extension period should sign the open-label extension period informed consent form at Week 110. Patients may also sign the OLE period informed consent form at Week 114, if not completed previously at Week 110.

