- d Includes clinical chemistry (serum sodium, potassium, chloride, bicarbonate, total protein, albumin, calcium, phosphate, glucose, cystatin, uric acid, BUN, creatinine [including calculation of eGFR], bilirubin [total, direct, and indirect], ALT, AST, ALP, gamma glutamyltransferase, creatine kinase, and amylase); hematology (red blood cells, hemoglobin, hematocrit, MCV, MCH, MCHC, platelets, WBC, and WBC differential [percentage and absolute: neutrophils, eosinophils, basophils, lymphocytes, and monocytes]); and routine urinalysis (color, appearance, and dipstick [pH, specific gravity, protein, glucose, ketones, bilirubin, blood, urobilinogen, and leukocyte esterase]). All chemistry and hematology analytes are shown in [Section 15.2.5](#).
- e Includes clinical chemistry (same as footnote d but excluding phosphate, cystatin, and uric acid); hematology (same as footnote d); and routine urinalysis (same as footnote d). It is strongly recommended that patients come to the study visit in a fasted state, and patients should remain fasted until their blood samples have been collected. If the patient has not been fasting, it should be documented accordingly in the eCRF.
- f Includes total cholesterol, LDL (direct), HDL (direct), and triglycerides (direct). Lipid analytes are shown in [Section 15.2.5](#)
- g Urine protein excretion and creatinine. Sample will be collected 24 hours immediately prior to the visit. Patients who forget to collect this sample 24 hours immediately prior to the visit may collect and return it within the visit window. Protein excretion and creatinine will be measured from this sample.
- h Patients will complete the KDQoL-36t. All patients will also complete the EQ-5D-5L. Patients participating in the OLE period who did not complete the questionnaires at Day 1 of the double-blind period should complete them at Week 114 (as baseline assessments for the OLE) and throughout the OLE.

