#### **6.4.2. Open-Label Extension Period Baseline**

OLE baseline is defined as the last nonmissing assessment prior to and including the first administration of sparsentan (including unscheduled assessments) in the open-label extension. In the case where the last nonmissing assessment and the sparsentan start date (and time if available) coincide that assessment will be considered baseline.

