## 8. EFFICACY

### 8.1. General Considerations

All efficacy analyses will be based on the FAS or PAS as described below. The primary and key secondary endpoint analyses will also be performed on the PP Analysis Set as supportive analyses. All primary efficacy analyses based on laboratory data will use central laboratory data only. All efficacy analyses specified below refer to the double-blind period only.

Proteinuria (UP/C) will be determined based on a 24-hour urine sample. As UP/C is a highly right-skewed variable, analyses will be performed on log-transformed data. For ease of interpretation, results will be presented in the original units.

The eGFR for each baseline and post-baseline visit will be determined using the Chronic Kidney Disease Epidemiology Collaboration ([Levey 2009](#)) formula for adults based on serum creatinine values from the visit.

For the purposes of efficacy analyses, an assessment is considered “on treatment” if it occurs after the first dose of study medication and no more than 3 days after the date of last dose of randomized treatment for the patient.

For all least squares (LS) means that include strata coefficients, the observed strata proportions will be used instead of assuming equal sizes of strata.

Longitudinal analyses of UP/C and eGFR (eg, via MMRM for continuous endpoints or generalized linear mixed models for binary endpoints) will consider data from post-baseline visits through Week 110 of the double-blind period. At the primary analysis, if there are issues with model converge due to sparsity of measurements at the later visits (ie, Week 106 or Week 110), then the longitudinal analyses will include only data through an earlier visit (ie, Week 94) to enable the analyses. The last visit to be included in the analyses will be appropriately documented in a note to file prior to unblinding for the primary analysis.

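### The late-collection rule for the 24-hour urine has no exception at Week 110/EOT or Week 114, where it does not fit the SAP's 3-day on-treatment rule, protocol Section 6.2.2 or the open-label baseline definition

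*Protocol*

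**What the plan says.** **Collection rule.** Protocol Table 15.1-2 marks the 24-hour urine at every visit from Week 48 to Week 114. Its footnote f states: "Patients who forget to collect this sample the 24 hours immediately prior to the visit may collect and return it within the visit window". Footnote g of Table 15.1-3, whose urine row also covers Weeks 110 and 114, says the same: "Patients who forget to collect this sample 24 hours immediately prior to the visit may collect and return it within the visit window". The visit windows are ±14 days at Week 110 and −7/+14 days at Week 114. Neither footnote treats these two visits differently from the others.

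**Week 110.** Protocol Section 6.2.1: "Following the 110-week blinded treatment period, treatment with study medication will be discontinued for 4 weeks". Standard of care, including a RAAS inhibitor, is resumed at that point. Under Section 6.3.2 study medication cannot be restarted once the EOT/ET visit is completed. Footnote a of Table 15.1-2 limits Week 110 evaluations only by the first open-label dose, not by the last blinded dose. SAP 6.5.4 restricts efficacy visits up to Week 110 to on-treatment assessments, and SAP 8.1 defines these as taken after first dose and "no more than 3 days after the date of last dose of randomized treatment for the patient".

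**Week 114.** Protocol Section 6.2.2: "All Week 114 (baseline visit) evaluations must be completed prior to the first dose of open-label sparsentan". SAP 6.4.2: "OLE baseline is defined as the last nonmissing assessment prior to and including the first administration of sparsentan". Protocol Section 6.1.4 defines the open-label UP/C endpoint as percent change from Week 114.

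**The concern.** At a mid-treatment visit, a urine collected some days late is still collected on the assigned drug, so the rule is harmless. Week 110 and Week 114 differ because treatment changes at the visit.

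At Week 110 the protocol tells sites that a sample up to the end of the window is acceptable, while the SAP discards most of those samples. The affected measures are change in UP/C, urine protein excretion, UA/C and urine albumin excretion at Week 110, the first four of the six ordered other secondary tests in SAP 8.4.3. SAP 8.7.3 does not use multiple imputation for them, so a discarded value is simply missing from the MMRM.

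At Week 114, for patients entering the extension, the footnotes permit a collection that Section 6.2.2 rules out. If no urine is obtained before the first open-label dose, SAP 6.4.2 as written falls back to the last earlier value. That is normally the Week 110 value, taken on blinded sparsentan or irbesartan, whereas patients with a Week 114 urine have a baseline on resumed standard of care. Open-label results are to be shown by original arm (protocol Section 12.11), and the effect of the fallback would differ by arm.

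**Working it through.** No sample size, power or alpha figure in the plan depends on this point. The check is arithmetic on study days, plus one illustration.

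**Target days and windows.** Target day = 7 × week + 1. Week 110: 7 × 110 + 1 = 771. Week 114: 7 × 114 + 1 = 799. Both match SAP Table 1. The protocol windows are therefore days 757–785 for Week 110 and days 792–813 for Week 114. The SAP window for the Week 110 urine is days 758–785; for Week 114 it is any day after 785.

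**Week 110.** Permitted late days run from the day after the visit to day 785. The SAP accepts a late day only if it is no later than last dose + 3. I date each collection by a single day, because SAP 8.1 does not say whether the start or the end of the 24 hours counts. With the last dose on the visit day:

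| Visit day | Permitted late days | Accepted | Discarded |
|---|---|---|---|
| 757 | 28 | 3 | 25 |
| 771 | 14 (772–785) | 3 (772–774) | 11 (775–785) |
| 778 | 7 | 3 | 4 |
| 784 | 1 | 1 | 0 |

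If the last dose was the day before a day-771 visit, 2 days are accepted and 12 discarded. All 11 discarded days in the main case lie inside the SAP's own Week 110 window, so the 3-day rule is what removes them.

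**Week 114.** If the visit and first open-label dose are on day 799, the footnotes permit collection until day 813, which is 813 − 799 = 14 days after that dose. If both are on day 792 the figure is 21 days, and on day 806 it is 7 days. Section 6.2.2 permits none of these days. SAP 6.4.2 excludes such a sample from the open-label baseline, but the Week 114 window in SAP Table 1 has no upper limit and no cut at the first open-label dose.

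**Illustration of the baseline fallback.** Assume the 30% relative effect on UP/C from the sample-size section, that this effect has fully gone by Week 114, and that resumed standard of care acts like irbesartan. An original-sparsentan patient whose baseline falls back to Week 110 then has a baseline 0.70 times the off-drug value, and ln 0.70 = −0.357. If a share m of that group falls back, the group geometric mean baseline drops by 1 − exp(m × ln 0.70):

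- m = 5%: 1 − exp(−0.0178) = 1.8%
- m = 10%: 1 − exp(−0.0357) = 3.5%
- m = 20%: 1 − exp(−0.0713) = 6.9%

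The ratio to baseline is then multiplied by 1/(1 − drop), which is 1.018, 1.036 and 1.074, so the change looks slightly less favourable. Under the same assumptions the original-irbesartan group has no comparable shift. The shares m are assumed; the documents give no rate of forgotten samples.

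**The case against.** Much of the case on the other side stands.

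A reader might infer that off-drug urine contaminates the Week 110 tests. The documents do not support that: SAP 6.5.4 and 8.1 keep out anything more than 3 days after last dose. The 3-day allowance itself is a prespecified tolerance applied to all efficacy analyses.

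A reader might also infer that a Week 114 sample taken on open-label sparsentan would serve as baseline. It would not: Section 6.2.2 requires evaluations before the first dose, and SAP 6.4.2 excludes later values. The footnotes are permissive, so they can be read together with Section 6.2.2 to mean that a forgotten urine is collected before that dose. Patients who do not enter the extension start no open-label drug at Week 114, so the conflict does not reach them.

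The footnote does not create the missing value either, since a forgotten sample is missing without it. The MMRM still uses the earlier visits, including Week 106, and the other secondary tests are reached only if all key secondary endpoints succeed.

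Open-label efficacy is left to a separate SAP (SAP 3.2.4 and 5.3), is descriptive, and may use other baselines (protocol Section 12.11). How that SAP will treat a missing Week 114 urine is not known.

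What remains is that the footnotes offer sites a rescue that the SAP mostly refuses at Week 110, that they contradict Section 6.2.2 at Week 114, and that the open-label baseline definition already written in this SAP permits the fallback.

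**Conclusion.** The point holds as a mismatch between rules, and it is minor. For a visit and last dose on day 771, samples on 11 of the 14 permitted late days would be lost from the four Week 110 urine tests. For patients entering the extension, the Week 114 rule conflicts with Section 6.2.2. SAP 6.4.2 as written would then mix on-drug and off-drug UP/C baselines, differently by original arm, for an endpoint defined as change from Week 114.

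The Week 36 primary endpoint is not affected, nor are the eGFR slopes, which come from serum creatinine. The number of patients concerned cannot be derived from the documents. The 1.8% to 6.9% shifts are illustrative only. They rest on assumed shares, on complete loss of the 30% effect by Week 114, and on resumed therapy acting like irbesartan. Any residual drug effect at Week 114 would make them smaller. To read them as an expected bias in the trial's results would go beyond what the documents support.

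**What to change.** 1. Reconcile footnotes f and g with the SAP on-treatment rule: a late Week 110 collection counts as Week 110 only if it falls within the SAP's limit of 3 days after last dose. Tell sites so. A stricter cut at the last blinded dose is not advised, because it would reject samples that the SAP accepts.
2. Reconcile the same footnotes with Section 6.2.2: for patients entering the extension, a Week 114 collection is valid only if completed before the first open-label dose.
3. In SAP 6.4.2, carried into the open-label SAP, require the UP/C baseline sample to fall after blinded drug was stopped and before the first open-label dose. Otherwise set the baseline to missing in the change-from-Week-114 summary.

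These changes settle only which sample counts; they alter no dose or dosing date. The cost is one sentence in each of two footnotes and one line in the SAP. At Week 110 no usable data are given up, since the SAP already drops the later samples. In the extension, a few baselines become missing in a descriptive summary.

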**Table 15.1-4. Open-label Extension Period: Schedules of Study Events from Week 198 Through End-of-Study**

Week	Open-label Treatment						
	Week 198	Week 210	Week 222	Week 234	Week 246	Week 258	Week 270 End-of-Study
Visit	24	25	26	27	28	29	30
Visit Window	± 28 days	± 28 days	± 28 days	± 28 days	± 28 days	± 28 days	± 28 days
Optional Informed Consent for SGLT2i Sub-Study (Baseline SGLT2i visit) and Randomizationj	As early as Week 126 (Visit 18) but no later than Week 258 (Visit 29)						
Full Physical Examination							
Targeted Physical Examination	X	X	X	X	X	X	X
Peripheral Edema Assessment a	X	X	X	X	X	X	X
Vital Signs b	X	X	X	X	X	X	X
Clinical Laboratory Assessments Panel A c	X	X	X	X	X	X	X
Lipid Panel d	X	X	X	X	X	X	X
NT-proBNP	X	X	X	X	X	X	X
Quantitative Urinalysis (24-hour collection) e	X	X	X	X	X	X	X
QoL Questionnaires f	X	X	X	X	X	X	X
Urine Pregnancy Test g	X	X	X	X	X	X	X
Dispense Urine Pregnancy Tests g	X	X	X	X	X	X	
Biorepository Samples (blood and urine, if consented)	X	X	X	X	X	X	X
Medication Dispensing h,i	X	X	X	X	X	X	
Study Medication Accountability k	X	X	X	X	X	X	X
Adverse Event Assessment	-----Continuous Monitoring-----						
Concomitant Medications/Therapies	-----Continuous Monitoring-----						

Abbreviations: ALP = alkaline phosphatase; ALT = alanine aminotransferase; AST = aspartate aminotransferase; BUN = blood urea nitrogen; eGFR = estimated glomerular filtration rate; EQ-5D-5L = EuroQol, 5-dimension 5-level QoL Questionnaire; ET = early termination; HDL = high-density lipoprotein; KDQoL-36 = Kidney Disease QoL Questionnaire; LDL = low-density lipoprotein; MCH = mean corpuscular hemoglobin; MCHC = mean corpuscular hemoglobin concentration; MCV = mean corpuscular volume; NT-proBNP = N-terminal prohormone of brain natriuretic peptide; SGLT2 = Sodium-glucose cotransporter-2; SmPC = summary of product characteristics; USPI = US prescribing information; WBC = white blood cell; WOCBP = women of childbearing potential

a Peripheral edema assessment guidance is provided in [Section 15.2.4](#).

b Vital signs should be measured prior to having blood drawn for laboratory evaluations. Blood pressure will be measured after patients have been sitting comfortably in a chair for at least 5 minutes prior to obtaining 3 readings using the same arm for each reading; the mean of the last 2 readings will then be recorded. Measurements of blood pressure intended to detect possible orthostatic hypotension will also be performed at each visit (see [Section 9.6](#)). For these measurements, blood pressure will be measured

- 3 times: 1 time after the patient has been in a supine position for 5 minutes, 1 time after the patient has been standing for 1 minute, and 1 time after the patient has been standing for 3 minutes. Weight, heart rate, temperature, and respiration rate will also be recorded. Heart rates will be measured with each positional blood pressure reading for orthostatic hypotension detection.
- c Includes clinical chemistry (serum sodium, potassium, chloride, bicarbonate, total protein, albumin, calcium, phosphate, glucose, cystatin, uric acid, BUN, creatinine [including calculation of eGFR], bilirubin [total, direct, and indirect], ALT, AST, ALP, gamma glutamyltransferase, creatine kinase, and amylase); hematology (red blood cells, hemoglobin, hematocrit, MCV, MCH, MCHC, platelets, WBC, and WBC differential [percentage and absolute: neutrophils, eosinophils, basophils, lymphocytes, and monocytes]), and routine urinalysis (color, appearance, and dipstick [pH, specific gravity, protein, glucose, ketones, bilirubin, blood, urobilinogen, and leukocyte esterase]). All chemistry, hematology, and urinalysis analytes are shown in [Section 15.2.5](#).
  - d Includes total cholesterol, LDL (direct), HDL (direct), and triglycerides (direct). Lipid analytes are shown in [Section 15.2.5](#)
  - e Urine protein excretion and creatinine. Sample will be collected 24 hours immediately prior to the visit. Patients who forget to collect this sample 24 hours immediately prior to the visit may collect and return it within the visit window. Protein excretion and creatinine will be measured from this sample.
  - f Patients will complete the KDQoL-36. All patients will also complete the EQ-5D-5L.
  - g Urine pregnancy tests will be dispensed to WOCBP to conduct pregnancy testing at home between study visits. Sites will provide the patients enough tests to conduct pregnancy testing once per month until the next scheduled study visit and will contact these patients monthly to confirm that the pregnancy test has been performed and the results are negative. A positive urine pregnancy test will be confirmed by a serum test.
  - h Dispense sparsentan. Patients will be instructed to take their sparsentan in the clinic on the day of office visits. On all other days, sparsentan should be taken at approximately the same time each day, preferably prior to the morning meal. Patients will be instructed to swallow the tablets whole and to not open, break, chew, crush, or split the tablet prior to taking. For each patient, the time when sparsentan was taken should be recorded in the eCRF. Patients will also be instructed to avoid drinking or eating anything that contains grapefruit, Seville oranges (bitter oranges often used as marmalade), starfruit (carambola), or pomelo/shaddock throughout the study. The patient will be instructed to bring all sparsentan tablets and their original containers to the next clinic visit.
  - i If patient is enrolled in the Sub-study and randomized to the SGLT2 inhibitor treatment group, Investigator will instruct patient on the dispensing, daily dose, and administration according to USPI, SmPC, or local label. The patient will be instructed to bring all packs (bottles or blister packs) to the next clinic visit.
  - j Patients enrolled in the Sub-study and randomized to receive SGLT2 inhibitors may have a safety visit between 7 to 14 days after beginning dosing with the SGLT2 inhibitor.
  - k This will be derived from medication dispensed to a patient in the Sub-study are returned.

